March 2023-April 2024	
Pilot baseline data collection.
 
Referrals that come in from March-Dec will have post-intervention data included in the pilot study primary outcome analysis. Referrals coming in Jan-April will have baseline data only included in the analyses to address the aims of the pilot study regarding recruitment and acceptability.
	AM & EC, with input from rest of Evaluation Team

May-June 2024
	
Transition.
 
Evaluators prepare draft report on pilot, for submission end of May. YEF make progression decision by late June.
	
SD, JR, with input from rest of Evaluation Team.
 
AM & EC, with input from rest of Evaluation Team

July 2024-Dec 2024
	
Reflect on feedback from report. Make any alterations necessary to procedures.
 
Efficacy baseline data collection.
 
IPE data collection.
	
AM & EC, with input from rest of Evaluation Team

Jan-April 2025
	
Efficacy post-intervention data collection
 
IPE data collection.
	
AM & EC, with input from rest of Evaluation Team

May-Dec 2025
	
Complete 3 month follow up data collection.
 
Complete IPE data collection.
 
Analysis and reporting.
	
AM & EC, with input from rest of Evaluation Team.
 
SD, JR, with input from rest of Evaluation Team.

References

- Adamsons, K., & Pasley, K. (2006). Coparenting following divorce and relationship dissolution. In M. Fine & J. Harvey (Eds.), *Handbook of Divorce and Relationship Dissolution*, pp. 241-262. Mahwah, NJ: Lawrence Erlbaum
- Altman, D.G. & Bland, M.J. (2005) Statistics Notes: Treatment allocation by minimisation. *BMJ* 330 p843
- Arnold, D. S., O'leary, S. G., Wolff, L. S., & Acker, M. M. (1993). The Parenting Scale: a measure of dysfunctional parenting in discipline situations. *Psychological Assessment*, 5(2), 137. <https://doi.org/10.1037/1040-3590.5.2.137>

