	Level 3 (cluster)	0.01 to 0.15	0.27
Alpha		0.05	0.05
Power		0.80	0.80
One-sided or two-sided?		Two	Two
Average cluster size		2 CYP per family	1.4 CYP per family
Number of clusters	Intervention	175	125
	Control	175	125
	Total	350	250
Number of participants (CYP)	Intervention	350	175
	Control	350	175
	Total	700	350

The power analyses published in the protocol included key parameters for which no empirical estimates could be obtained. Specifically, these were covariate explanatory power (from the baseline mothers SDQ measure) at CYP and family levels and the family level ICC for the mothers SDQ measure at outcome. The protocol used relatively wide ranges of values for CYP and family level explanatory power (between 0.25 and 0.49) and ICC (0.01 to 0.15).

As specified in the protocol, analyses of data from the internal pilot provides empirical point estimates for these parameters for use in the updated power analyses presented here. At the time of writing (August 2024), a total of 43 families (21 allocated to MBT and 22 to TAU) with 61 CYP (30 MBT, 31 TAU) had complete baseline/T1 and outcome (T2, post intervention) mothers SDQ. Analyses of these 61 CYP in 43 families has been used to provide empirical estimates for ICC and explanatory power at the family and CYP levels.

The power analyses were undertaken using equation 1.0 below and checked using the PowerUp! software (Dong & Maynard, 2013, sheet CRA2_2r).

$$[1.0] \quad MDES_{2LCRT} \sim M_{J-m-2} \sqrt{\frac{1}{P(1-P)}} \sqrt{\frac{ICC(1-R_{Fam}^2)}{J} + \frac{(1-ICC)(1-R_{CYP}^2)}{nJ}}$$

For a 2-level CRT design, the MDES is influenced by (estimates updated from analyses of pilot data):

- n=number of CYP per family = **1.4** (updated from 2.0 in protocol).
- J = number of families (**90** at pilot, allowed to vary up to **400** see below).
- P = proportion of families allocated to intervention group (= **0.50**).
- m= number of (level 2) covariates used (which will include: group membership, family-level pre-test, 4 (dummy) variables used for minimisation ~ **6** variables).
- M_{J-m-2} is the group effect multiplier value of the t-distribution for a 2-tailed test with alpha=0.05 & beta=0.80.
- ICC is the family level ICC = **0.27** (updated from 0.01 to 0.15 in protocol). This is the proportion of variance of the outcome at level 2 (between-family variance).

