The updated power analyses presented here illustrate that, even with fewer CYP per family than initially estimated, a smaller sample of families is likely to be sufficient sensitivity to detect an MDES of 0.20 sds or higher than was estimated at protocol. With 250 families (and 350 CYP), the MDES estimate is 0.17 sds. With an attrition rate of 10%, assuming attrition was random, the indicative MDES estimate is 0.18 sds. With an attrition rate of 20%, assuming attrition was random, the indicative MDES estimate is 0.19 sds.

Therefore, following the updated power analysis, the recommended sample size for the evaluation of the Tavistock MBT-PP programme is reduced from 350 families (700 CYP) to be 250 families (350 CYP).

Analysis

Research questions were operationalised as follows:

RQ1 Does MBT-PP (compared to TAU) delivered to parents experiencing IPC lead to lower externalising and internalising behaviours in children aged 8-14 (as measured by the SDQ total 'difficulties' scale)?

This splits into two separate RQs (SDQ total difficulties for mothers and for fathers).

RQ1a Does MBT-PP (compared to TAU) delivered to parents experiencing IPC lead to lower externalising and internalising behaviours in children aged 8-14 as measured by the mother's SDQ total 'difficulties' scale? – PRIMARY OUTCOME RQ1

RQ1b Does MBT-PP (compared to TAU) delivered to parents experiencing IPC lead to lower externalising and internalising behaviours in children aged 8-14 as measured by the father's SDQ total 'difficulties' scale? – SECONDARY OUTCOME RQ1

RQs 2-8 inclusive also all examine secondary outcomes, and, apart from those where the outcome variable comes from CYP rather than parents (RQ2 regarding child wellbeing and RQ4 regarding child perception of IPC), they split into a) maternal report and b) paternal report, as per RQ1.

RQ2 Does MBT-PP (compared to TAU) delivered to parents experiencing IPC lead to higher wellbeing in children aged 8-14 (as measured by the Stirling Children's Well-being Scale)?

RQ3 Does MBT-PP (compared to TAU) delivered to parents experiencing IPC lead to lower IPC reported by parents (as measured by the O-Leary-Porter Scale)?

RQ3a Does MBT-PP (compared to TAU) delivered to parents experiencing IPC lead to lower IPC reported by mothers (as measured by the O-Leary-Porter Scale)?

RQ3b Does MBT-PP (compared to TAU) delivered to parents experiencing IPC lead to lower IPC reported by fathers (as measured by the O-Leary-Porter Scale)?

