The analysis described in this plan follows YEF analysis guidance¹. An Intention to Treat (ITT) approach will be taken whereby CYP are identified as members of the intervention or control group solely based on their random allocation and regardless of whether their parent(s) participate in the intervention or not. The ITT approach best preserves random allocation. This means that the only difference between the two group (of families/parents) is that one group received the Tavistock MBT-PP programme and the other groups (TAU) did not. All other differences between these groups are (fixed to be) random at baseline and, assuming zero attrition, this assumption is maintained at outcome. It is the ITT analysis of the primary outcome (mothers reported SDQ total difficulties score) that this clustered RCT is statistically powered to detect. Specifically and assuming zero attrition, if a difference between the intervention and control group is observed to be 0.17 sds or higher, this would represent evidence that participation in the Tavistock programme caused this positive (or negative) impact within pre-specified levels of statistical significance ($p < 0.05$, two-tailed) and statistical power (0.80 or higher). As detailed below, following the ITT analysis of the primary outcome, missing data and Compliers Average Causal Effect (CACE) analyses will be undertaken.

An ITT approach will also be used for analyses of secondary outcomes. Follow-on analyses of the primary outcome will estimate the Compliers Average Causal Effect (CACE); the impact of the programme for CYP located in families/parents known to have engaged in the MBT-PP programme as was intended (see below).

All analyses will be undertaken using STATA v18. Specifically, parameter estimates will be obtained using the 'mixed' suite of commands in the STATA software. For primary and secondary outcomes, pre-test covariates will be included at both CYP and cluster (family) levels. These will be centred as recommended by Hedges & Hedberg (2007 & 2013) and Konstantopoulos (2008). Specifically, at the CYP level, scores will be centred around the cluster (family/parent) mean and at the family/parent level the cluster(family) means will be centred around the overall cluster-level grand mean. Other than the constant term, centring

¹ <https://youthendowmentfund.org.uk/resources-for-evaluators/>

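### The 0.17 SD detectable effect behind the cut to 250 families is shown without pilot uncertainty or observed attrition, and is then misread as the observed difference that counts as evidence

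*SAP*

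**What the plan says.** **Inputs.** The protocol (Sample size calculations, Table 4) used ranges: ICC 0.01 to 0.15, and R² 0.25 to 0.49 at both levels. The SAP (Sample size calculations) replaces them with single values from the pilot: ICC 0.27, child-level R² 0.75, family-level R² 0.61. On the source it says: "Analyses of these 61 CYP in 43 families has been used to provide empirical estimates for ICC and explanatory power". Family size is also updated: "n=number of CYP per family = 1.4 (updated from 2.0 in protocol".

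**Result.** "With 250 families (and 350 CYP), the MDES estimate is 0.17 sds". The SAP adds 0.18 at 10% attrition and 0.19 at 20%, and on that basis reduces the target from 350 to 250 families.

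**Pilot size.** The parameter list under equation 1.0 has "J = number of families (90 at pilot" and does not define that 90 further. The 43 families with complete mothers' SDQ at T1 and T2 are as of August 2024. The protocol Timeline puts pilot baseline collection in "March 2023-April 2024".

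**Use of the figure.** The intention-to-treat paragraph of the SAP Analysis section says, under an assumption of zero attrition: "if a difference between the intervention and control group is observed to be 0.17 sds or higher, this would represent evidence", at the pre-specified significance level and power.

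**Target.** The protocol (Assumptions) recommends 350 families to reach an MDES of 0.22 SD. The SAP says the protocol sample was set to detect 0.20 and works to 0.20.

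**The concern.** Three matters bear on how far the 0.17 can be relied on.

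1. **Precision of the inputs.** With 61 children in 43 families there are 61 − 43 = 18 within-family degrees of freedom, and at most 18 families with more than one child. The family ICC and the split of R² between levels are learned from those families alone. The SAP gives no interval and no sensitivity grid for them.
2. **Attrition.** Signs of problematic attrition and adjustment of the sample size estimates were both pilot aims (protocol, Internal Pilot Study, aims c and d). Attrition of the parent who supplies the primary outcome is progression criterion 9(i) in Appendix A, with an amber band up to 30%. The SAP updates family size, ICC and R² from the pilot, but reports and uses no observed attrition. In addition, a family can join with one parent (Consent procedure), and the father's SDQ may not replace the mother's in the primary analysis (Primary outcome). Families with no participating mother therefore count as randomised but not as analysed.
3. **Meaning of the MDES.** It is a true effect that the design would detect with 80% power. It is not the observed difference at which a result becomes significant.

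At stake are the stated justification for removing 100 families and the reading of the primary result if the estimate lies between about 0.12 and 0.17 SD.

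**Working it through.** **Inputs (SAP parameter list and Table 2).** ICC = 0.27; R²_Fam = 0.61; R²_CYP = 0.75; n = 1.4; m = 6. Allocation: "P = proportion of families allocated to intervention group (= 0.50"). Multiplier: "is the group effect multiplier value of the t-distribution for a 2-tailed test with alpha=0.05 & beta=0.80", where the 0.80 is the power.

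**Formula (SAP equation 1.0).** SE = √[1/(P(1−P))] × √[ICC(1−R²_Fam)/J + (1−ICC)(1−R²_CYP)/(nJ)]; MDES = M × SE, with M = t(0.975) + t(0.80) on J − m − 2 degrees of freedom.

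**Reproducing the SAP figure, J = 250.**
- Family term: 0.27 × 0.39 = 0.1053
- Child term: 0.73 × 0.25 / 1.4 = 0.1304
- SE = 2 × √(0.2357/250) = 0.0614
- M on 242 df = 2.813
- MDES = 2.813 × 0.0614 = **0.1727**, as stated

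The rest of the SAP column of Table 3 also reproduces, as do 0.182 at 10% loss (225 families) and 0.193 at 20% (200 families).

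**Sensitivity to R² at J = 250, ICC 0.27, n = 1.4.**
- R² = 0.49 at both levels: 0.27 × 0.51 + 0.73 × 0.51/1.4 = 0.4036; SE = 2 × √(0.4036/250) = 0.0804; MDES = **0.226**
- R² = 0.25 at both levels: 0.27 × 0.75 + 0.73 × 0.75/1.4 = 0.5936; SE = 0.0975; MDES = **0.274**

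**Sampling uncertainty of the pilot estimates.** The SAP does not give the family composition, so it has to be assumed. Data were simulated at the SAP's parameters for 43 families and 61 children under two mixes:

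| Assumed mix | 95% range of ICC | 95% range of MDES at 250 families |
|---|---|---|
| 27 one-child, 14 two-child, 2 three-child | 0 to 0.66 | 0.134 to 0.218 |
| 25 one-child, 18 two-child | 0 to 0.63 | about 0.13 to 0.22 |

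Under the second mix R²_CYP ranged from 0.48 to 0.89, and R²_Fam was essentially not identified. All of this is before attrition.

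**Attrition, taking the SAP's point estimates as true.** Smallest significant difference = t(0.975) × SE.

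| Families analysed of 250 | MDES | Power for 0.20 SD | Smallest significant observed difference |
|---|---|---|---|
| 250 (100%) | 0.173 | 0.90 | 0.121 |
| 225 (90%) | 0.182 | 0.87 | 0.128 |
| 200 (80%) | 0.193 | 0.83 | 0.135 |
| 175 (70%) | 0.207 | 0.77 | 0.145 |
| 150 (60%) | 0.224 | 0.71 | 0.157 |
| 125 (50%) | 0.245 | 0.63 | 0.172 |

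An MDES of 0.20 or less needs 187 analysed families (187/250 = 75%). One of 0.22 or less needs 155 (62%).

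**Observed-difference threshold.** With 250 families analysed, 1.970 × 0.0614 = **0.121 SD** reaches p < 0.05. An observed 0.17 gives t = 0.17/0.0614 = 2.77, p = 0.006. With 125 families analysed the threshold is 0.172, so an observed 0.17 would not be significant.

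**The case against.** The case for the SAP is substantial.

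- **Updating was planned.** The protocol said in advance that pilot estimates would replace its assumptions, and SAP Table 3 prints the protocol-based range (0.18 to 0.24 at 250 families) beside the new figure. This stands. The gap is the missing uncertainty, not the update.
- **The uncertainty range is not damning.** In a run of 400 simulated data sets, about 10% gave an MDES above 0.20 and about 2% above 0.22, before attrition. The SAP itself says only that the smaller sample is likely to suffice. This also stands.
- **The R² = 0.49 and 0.25 scenarios are pessimistic.** They pair the pilot ICC with R² below both pilot estimates. That is fair: they mark sensitivity and are not forecasts.
- **Attrition is not ignored.** The SAP shows 10% and 20%. What remains is that neither level is tied to pilot data, and that nothing reaches the protocol's own amber limit of 30%.
- **The evidence sentence is a sufficient condition.** It assumes zero attrition, and at 250 families an observed 0.17 is clearly significant, so it creates no false positive there. The Presentation of outcomes section also reports a 95% CI. This limits the damage, but the sentence still puts an observed difference where a true effect belongs.

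A reader might also divide 43 by 90 and infer that the pilot's completion rate was 48%. The documents do not support that. The 90 is not defined as randomised, as having an enrolled mother, or as due at T2. Referrals were to continue through the transition after the pilot, and January to April 2024 referrals were expected to give baseline data only to the pilot analysis. Sixteen weeks from the end of April falls in late August, so late recruits may not have been due. The 43 against 90 is a snapshot that calls for the proper denominator.

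**Conclusion.** The 0.17 SD is correctly calculated but presented with more certainty than 43 families can give. A fair statement is about 0.13 to 0.22 SD at 250 families before attrition, conditional on an assumed family mix. The attrition display stops at 20%; on the SAP's point estimates the 0.20 target is lost once more than about 25% of families are missing, and families without a participating mother add to that loss. These points do not establish that 250 families is inadequate, particularly against the protocol's 0.22.

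The evidence sentence in the Analysis section is wrong as written. On the SAP's inputs the smallest significant observed difference is about 0.121 SD with 250 families analysed, so an estimate of 0.12 to 0.17 could be misread as falling short. With about 125 or fewer analysed, an observed 0.17 would not be significant. Both thresholds depend on the same pilot estimates, so they illustrate the error and should not become decision rules.

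**What to change.** No extra enrolment is needed; these are changes to the SAP text and tables.

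1. **Analysis section.** State that evidence is judged by the p-value and 95% CI of β₁ in equation 2.0. Describe 0.17 only as the true effect detectable with 80% power if all 250 families are analysed and the pilot estimates hold. Do not substitute 0.12 as a new threshold.
2. **Tables 2 and 3 and the closing sample size text.** Give 0.17 with its pilot-uncertainty range, or a grid of ICC and R² against attrition running to at least 30% loss.
3. **Pilot attrition.** Report, by arm, the pilot families randomised, due at T2, and complete on mothers' T1 and T2 SDQ, and give the MDES at that observed rate.
4. **Target effect.** Reconcile 0.22 (protocol) with 0.20 (SAP), and state the number of analysed families it requires, conditional on the pilot estimates: about 187 for 0.20, about 155 for 0.22.

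The cost is some redrafting and, probably, a less favourable stated figure.
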